#### 11. Event reporting

#### 11.1 Adverse Events

An Adverse Event [AE] is defined as any unfavorable and unintended sign (including abnormal laboratory finding), symptom, or disease temporally associated with the use of a medical treatment or procedure, regardless of whether it is considered related to the medical treatment or procedure (attribution of unrelated, unlikely, possible, probable or definite). An unanticipated event is defined as any adverse experience where the nature, severity or frequency is not described in the application form or detailed in the consent form. This can also include non-compliance issues such as over enrollment of subjects without prior COMIRB approval.

The causal relationship to study treatment will be determined by the PI and used to assess all AEs and unanticipated problems. The causal relationship can be one of the following:

**Possibly related**: In the opinion of the PI, the adverse event is unlikely to be related to the study intervention, drug or device.

**Probably related**: In the opinion of the PI, it is more likely than not that the adverse event is related to the study intervention, drug or device.

**Related to the research**: An event is "related to the research procedures" if in the opinion of the principal investigator, it was more likely than not [probably] to be caused by the research procedures or if it is more likely that not [probably] that the event affects the rights and welfare of current participants.

The PI will report any unexpected event that is deemed to be probably related or related to the research within 5 days, per COMIRB's policy.

The risks associated with the ultrasonic aspirator and the CO2 laser ablation devices are similar with the exception that early studies suggest scarring may be significantly decreased with the use of the ultrasonic aspirator. [1] Previous studies have also suggested that the ultrasonic aspirator will have less recurrence of dysplasia following treatment. [3]Since these early studies have failed to provide significant power, this is only hypothesized at this time and is the primary outcome for this phase III study.

Adverse events that are deemed not related will be documented in the study AE log, subject study charts, and reported to COMIRB at the time of annual review,

per their policy. The coordinating site will review AEs at interim analysis. Anticipated clinical adverse events may include:

- Pain and/or discomfort (~25% of women)

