- Presence of scarring (~30% of women receiving CO2 laser, less than 5% in women receiving ultrasonic aspirator)
- Dysureia or burning (~25% of women)
- Adhesions (less than 5%)
- Infection: yeast, UTI, or other (~10% of women)
- Abnormal discharge (less than 10% of women)
- Eschar (~10% of women). [1]

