# 11.2 Serious Adverse Event

A Serious Adverse Event (SAE) is any untoward medical occurrence at any dose that:

- Results in death
- Is life-threatening (defined as an event in which the subject was at risk of death at the time of the event; it does not refer to an event which hypothetically might have caused death if it were more severe)
- Requires inpatient hospitalization or causes prolongation of existing hospitalization (see *NOTE*\*: below for exceptions)
- Results in persistent or significant disability/incapacity
- Is a congenital anomaly/birth defect
- Is an important medical event, defined as a medical event that may not be immediately life-threatening or result in death or hospitalization but, based on appropriate medical and scientific judgment, may jeopardize the subject or may require intervention (e.g., medical, surgical) to prevent one of the other serious outcomes listed above

Suspected transmission of an infectious agent (e.g., pathogenic or non-pathogenic) via the study treatment is an SAE.

\*NOTE: The following hospitalizations are not considered SAEs:

- A visit to the emergency room or other hospital department lasting less than 24 hours that does not result in admission (unless considered an "important medical event" or a life-threatening event)
- Elective surgery planned before signing consent
- Admissions as per protocol for a planned medical/surgical procedure
- Routine health assessment requiring admission for baseline/trending of health status (e.g., routine colonoscopy)
- Medical/surgical admission other than remedying ill health state that was planned before study entry. Appropriate documentation is required in these cases
- Admission encountered for another life circumstance that carries no bearing on health status and requires no medical/surgical intervention (e.g., lack of housing, economic inadequacy, caregiver respite, family circumstances, administrative reason)

Participants experiencing a SAE should be discontinued from the study and followed per clinical standard of care. SAEs should be documented on the AE CRF and reported to local IRB and the coordinating site within 48 hours of notification of event.

There are no known reports of serious adverse events following CO2 laser and ultrasonic aspiration for vulva dysplasia.

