## 14. Statistical Analysis

A per protocol analysis will be conducted. Participants receiving treatment per protocol will be included in the final analysis. Investigators will not have the option to change treatment assignment.

Descriptive statistics using means, frequencies, and percentages will be computed to describe the study population. Participant data will be analyzed employing the per protocol approach. Student's *t*-test (for continuous variables) and chi-square tests (for categorical variables) will be used to compare the two groups for demographic, and secondary outcome variables: pain, scarring, QOL scores. For the primary outcome measure rate of recurrence for each of the study endpoints, 3 months, 6 months and 12 months will be calculated per treatment arm and compared with initial bivariate analysis using chi-square analysis. Additional predictors for recurrence (pain, scarring, sexual function, and general wellness) will be compared similarly with chi-square for categorical variables and t-tests for continuous variables. Potential covariates (age, race, previous disease, etc.) will also be analyzed using bi-variate analysis. Variables found to be significant in the bivariate analysis will be included in multivariable analysis using logistic regression. Logistic regression models will be used to identify significant independent predictors associated with recurrence for each treatment arm. The logistic model will allow for control of study covariates. A p-value of <0.05 will be used to demonstrate statistical significance. IBM SPSS version 22 will be used for all statistical analyses.

Incidence of AEs and SAEs will be compared between treatment arms using chisquare analysis. A p-value of <0.05 will be used to demonstrate statistical significance.

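### Minor: adverse events are compared by chi-square at p<0.05 without a stated number of tests or a descriptive label, and for the rare events that test says little

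*Combined protocol and SAP*

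**What the plan says.** Section 14 (Statistical Analysis) closes with two sentences on safety: "Incidence of AEs and SAEs will be compared between treatment arms using chisquare analysis", then "A p-value of <0.05 will be used to demonstrate statistical significance". The second repeats the rule that the preceding paragraph sets for the efficacy analyses. The section gives no number of tests, no multiplicity rule and no statement that the safety comparisons are descriptive or exploratory. Nor does any other section.

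Section 11.1 lists seven anticipated event types, most with one expected rate for all women, for example "Pain and/or discomfort (~25% of women", "Dysureia or burning (~25% of women", "Infection: yeast, UTI, or other (~10% of women" and "Adhesions (less than 5" percent. Abnormal discharge (under 10%) and eschar (about 10%) complete that group. Scarring alone has a separate rate for each arm: "Presence of scarring (~30% of women receiving CO2 laser, less than 5% in women receiving ultrasonic aspirator".

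Section 2.1 (Hypothesis 2) predicts less pain and less scarring with ultrasonic aspiration, and section 14.2 makes both secondary endpoints. On serious events, section 11.2 says: "There are no known reports of serious adverse events following CO2 laser and ultrasonic aspiration for vulva dysplasia".

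**The concern.** There are two separate weaknesses.

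The first is an open family of tests. With the number of comparisons unspecified, anything from two overall tests to one test per event type fits the text, and any p<0.05 may be presented as a demonstrated difference. The choice can be made after the data are seen. This matters somewhat more than usual here. One device is made by the sponsor (section 7.1), the sponsor could profit (section 15.4), and section 7.1 describes blinding only for the analysing statistician.

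The second is that a p-value is a poor summary of rare harms in a trial of this size. With 62 to 75 women per arm, a chi-square test on adhesions or SAEs has little chance of detecting even a doubling. A bare p-value does not show the reader how much harm remains compatible with the data.

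**Working it through.** **The plan's own figure.** The plan states only the per-test threshold of 0.05. It gives no family-wise error rate for safety, so there is none to reproduce.

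**Inputs.**
- 62 evaluable and 75 enrolled women per arm (section 6.2). The number in the safety comparison is not stated, so both are used.
- Event rates from section 11.1: dysuria or burning 25%, adhesions 5%, infection 10%, discharge 10%, eschar 10%. Adhesions and discharge are given as upper bounds and are taken at the bound.
- Pain and scarring are left out of the count of true nulls. Hypothesis 2 predicts a difference in both, and section 11.1 gives scarring different rates by arm. At 30% against 5%, power for scarring is 96% (62 per arm) or 99% (75 per arm), so a significant result there would be expected and would not be a false finding.

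**Chance of at least one false difference, one test per event type.**

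For k independent tests at exactly 0.05 the formula is 1 − 0.95^k. With k = 5: 1 − 0.95^5 = 0.226.

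The exact size of each uncorrected chi-square test, with equal rates in both arms, gives:

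| Event | 62 per arm | 75 per arm |
|---|---|---|
| Dysuria or burning (25%) | 0.0492 | 0.0493 |
| Adhesions (5%) | 0.0463 | 0.0488 |
| Infection, discharge, eschar (10% each) | 0.0506 | 0.0513 |

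- 62 per arm: 1 − 0.9508 × 0.9537 × 0.9494^3 = 0.224.
- 75 per arm: 1 − 0.9507 × 0.9512 × 0.9487^3 = 0.228.

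Events in the same woman are likely to be related. Simulating the five events from latent normal variables with common correlation 0, 0.5 and 0.8 (assumed values) at 62 per arm gave 0.23, 0.22 and 0.18. The range is therefore about 0.18 to 0.23.

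A continuity correction or Fisher's exact test has smaller sizes, identical for the two methods here:
- 62 per arm: 0.0309, 0.0112 and 0.0225 (three times), so 1 − 0.9691 × 0.9888 × 0.9775^3 = 0.105.
- 75 per arm: 0.0323, 0.0149 and 0.0269 (three times), so 1 − 0.9677 × 0.9851 × 0.9731^3 = 0.12.

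**Two overall tests only (any AE, any SAE).** 1 − 0.95^2 = 0.0975 at most. If SAEs are almost absent, their test almost never rejects, and the total is near 0.05.

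**Rare events.**
- Expected adhesions per arm at 5%: 62 × 0.05 = 3.1 and 75 × 0.05 = 3.75. Both are below 4, where the chi-square approximation is poor.
- Exact power of uncorrected chi-square for adhesions at 5% against 10% (the 10% is an assumption): 18% at 62 per arm, 22% at 75.
- Three SAEs against none: chi-square = 3 × 2n / (2n − 3). At n = 62 this is 372/121 = 3.07; at n = 75 it is 450/147 = 3.06. Both give p = 0.08.
- No SAEs in an arm: the exact two-sided 95% upper limit is 1 − 0.025^(1/n), which is 5.8% at n = 62 and 4.8% at n = 75.

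**The case against.** The strongest reply is that the plan never says it will test each event type. Section 14 speaks only of AE and SAE incidence, and section 11.1 is a list of anticipated risks, not of planned tests. Under the two-test reading there is little inflation. This stands, and it is why the size must be given under both readings.

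A reader might go further and count all seven listed events: 1 − 0.95^7 = 0.30, or a false safety difference in about three trials in ten. The documents do not support that as an expected rate. It requires per-event testing and seven true nulls, while the plan itself expects scarring to differ and hypothesises less pain. A reader might also infer that pain and scarring will be tested a second time as adverse events. The plan does not say so.

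A reader might likewise infer that a non-significant result on a rare harm will be taken as no difference. Section 14 says what p<0.05 demonstrates and gives no rule for larger p-values, and no equivalence or non-inferiority claim on safety appears. What stands is narrower: the chosen test is uninformative for such events.

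Three further replies have weight. Chance findings fall in either direction: for five independent true nulls, the chance of one or more favouring the sponsor's device is about 1 − 0.975^5 = 0.12. Apart from pain and scarring, AE incidence is not an objective or endpoint. Safety action during the trial rests on review by an independent safety officer with authority to suspend or close it (section 13.2), not on this p-value. Finally, unadjusted AE comparisons are common and favour sensitivity to harm. These points keep the matter minor. They do not justify attaching a demonstration of significance to an unspecified set of tests.

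**Conclusion.** The point holds as a minor one. The safety paragraph of section 14 sets a significance rule without fixing the number of tests or labelling them descriptive. The consequence depends on how it is read: about 0.18 to 0.23 for at least one false difference among five events if each is tested with uncorrected chi-square, about 0.10 to 0.12 for independent events with a continuity correction or Fisher's exact test, and at most about 0.10 (nearer 0.05) if only two overall tests are run.

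These figures assume equal true rates in both arms at the values in section 11.1, with adhesions and discharge at their upper bounds. Rarer events would lower them: at a 1% adhesion rate and 62 per arm, that test's size falls to 0.004.

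The rare-event weakness does not depend on how many tests are run. Its power figure rests on the assumed 10% comparison rate; the upper limits for zero SAEs rest only on the arm sizes. The primary analysis, the sample size and safety oversight are unaffected.

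**What to change.** Replace the last paragraph of section 14 with wording such as:

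> AE and SAE incidence will be summarised by treatment arm as the number and percentage of women with each event type, with the risk difference and an exact or score 95% confidence interval. These comparisons are descriptive. No p-value threshold will be used to claim a difference in safety. Claims about pain and scarring rest only on the secondary endpoints in section 14.2.

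This costs one paragraph and a standard safety table, with no new data and no change to sample size or trial conduct. The downside is that the sponsor could not claim a statistically significant safety advantage from the AE table.

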## 14.1 **Primary Endpoint**

The primary endpoint for the study is recurrence of vulvar dysplasia. Recurrence will be assessed by physical exam and colposcopy. Further exam by biopsy will used to assess recurrence when appropriate, per provider's discretion. All clinical guidelines for referring to colposcopy should be followed, per standard of care.

## 14.2 Secondary Endpoints

The secondary endpoints for this study are as follows:

Pain: Pain in the initial 7-10 days following treatment will be self-assessed using a pain scale. Average pain scores and incidence of high-level of pain will be determined for each treatment arm.

Scarring: Scarring in the 6 weeks following treatment will be assessed via visual exam by a study investigator. Incidence rates of scarring will be determined for each treatment arm.

Sexual function and sexual distraught: Sexual function and distraught will be assessed at baseline, 6, and 12 months following treatment. Mean scores for

function and distraught will be determined for each treatment arm per study time-point. Sexual function and distraught will be measured with validated instruments, The Female Sexual Function Index, and the Female Sexual Distress survey (Appendix 1.3 and 1.4).

Wellness and Function: General wellness and function will be assessed at baseline, 6, and 12 months following treatment. Mean scores for general function will be determined for each treatment arm per study time-point. Wellness will be measured using the validated instrument FACTS survey for vulvar malignancies (Appendix 1.2).

# 15. Study Management

# **15.1** Compliance with the Protocol

The study shall be conducted as described in this approved protocol. All revisions to the protocol must be reviewed by the study investigators and appropriate collaborators. The investigator will not implement any deviation or change to the protocol without prior review and documented approval from the IRB of an amendment, except where necessary to eliminate an immediate hazard(s) to study subjects.

# 15.1.1 Protocol Amendments

Any amendments to the protocol will be first reviewed by the study team and then submitted to the IRB of the lead site for approval. Sub-sites will then be required to submit the protocol amendment to their local IRB and maintain all submission and approvals in their regulatory files. Sites will not initiate any changes to study procedures until after approval of the protocol amendment by their local IRB. Insignificant changes (i.e. personnel changes) may not have to be submitted to the sponsor and/or lead site first.

# 15.1.2 Subject Withdrawals

All participant documentation up until study withdrawal will be maintained and used for data analysis. In the event a participant is lost to follow-up, 3 documented attempts will be made to contact the participant to conduct an end of treatment visit. If after 3 attempts, the participant still does not return, a certified letter noting withdraw from study should be sent to the participant. The study coordinator will maintain a return receipt for such. Additionally, the study coordinator should send a self-addressed package to the participant for return of any study medications and/or study documents.

# 15.1.3 Participant Confidentiality

Data obtained during conduct of this study is to remain confidential and private. Participant confidentiality must be obtained in accordance to regulations set forth by Good Clinical Practice and HIPAA. Release of study data should only be done through the publication/presentation of results, lead by the Principal Investigator (PI). Study sites should not release any confidential data or findings of this study without the consent of the PI and the study sponsor.

# 15.1.4 Clinical Monitoring

Clinical monitoring of the study will be conducted by research personnel (data manager) from the University of Colorado Denver for all additional sites. The University of Colorado will conduct their own audit and validation of study entry with internal research personnel through the Clinical Research Support Center. In order to conduct monitoring, study sites should make staff and resources available for the following:

- Initial in-service of the study site, including investigator training and site tour
- Regular attendance of progress meetings
- Research staff available for interim monitoring visits
- All study documents (consents, CRFs, et) available for site visits in which the monitor will verify accuracy of data as entered into the electronic database
- Response to data requests via fax/email if site visit is not necessitated
- Maintenance of all regulatory documents and accessible for monitor review (UCD may request these be sent to the lead site for regulatory maintenance)

• Research staff available to response to data queries and resolve inconsistencies in study records

• Close out of the study at the study site

The study monitor will provide each site with a report of the monitoring visit to be submitted to their local IRB. In addition to monitoring visits, a monthly conference call will take place among all sites to discuss treatment outcomes, enrollment, significant toxicities, dose modifications, and responses. These meetings will be documents and the minutes shared with all sites.

Additionally, the University of Colorado DSMC may request a site audit to evaluate conduct and compliance of the investigational protocol as a study site. All study documents and regulatory documents must be available to audit. The audit reviewer will also require direct access to study source (participant medical records relating to study) and time with the site investigator and/or regulatory personnel during their visit.

## 15.2 Records Retention

Study documents will be retained for 7 years after the IRB acknowledgement of study closure, per HIPAA regulations.

All study documentation should remain on study site in a secured area with limited access.

The investigator must retain all study records and source documents for the maximum period required by applicable regulations and guidelines, or institution procedures, or for the period specified by UCD, whichever is longer.

If the investigator withdraws from the study (e.g. relocation, retirement), the records shall be transferred to a mutually agreed upon designee (e.g. another investigator, IRB). Notice of such transfer will be given in writing to the study sponsor.

15.2.1 Research Electronic Data Capture

15.2.2. Data Management

# 15.2.3 Confidentiality and Reporting of Results

The information on individual subjects arising from this study is to be considered confidential and transmitted to the sponsor only in a form that will not permit identification of the individual. The information obtained from the subjects that can be identified with the subject will remain confidential within the research team. Research teams will maintain all records in a secure area with limited access. Regulatory and sponsoring agencies may request access to the study records and related medical records of each participating subject. If requested, the subject's identity will remain confidential to the extent permitted by the applicable laws and regulations. The results of the research will be released to public agencies including regulatory agencies, clinical investigators, and research organizations without reference to items identifiable to a particular subject. The results will be published such that the identity of the subjects will not be disclosed and cannot be ascertained.

# 15.3 Publication Policy

Data on the use of the study interventions and results of all clinical study are considered confidential. UCD will lead any publication of the results of the study. Any publications or presentations that result from this study will maintain confidentiality of study participants.

# 15.4 Conflict of Interest

Investigators will be affiliated with their study sites and have no affiliation with the sponsoring agency. They will receive support for this clinical trial from the study sponsor but will not profit from results, either positive or negative, with regard to the product being evaluated. The sponsoring agent could profit from the successful development of this product.

Appendix 1: Survey Instruments

Appendix 1.1 Pain Assessment Scale

Appendix 1.2 FACT-V (Version 4)

# For Vulva Cancer diagnosis only

Below is a list of statements that other people with your illness have said are important. Please circle or mark one number per line to indicate your response as it applies to the past 7 days.

	PHYSICAL WELL-BEING	Not at all	A little bit	Some -what	Quite a bit	Very much
GP1	I have a lack of energy	0	1	2	3	4
GP2	I have nausea	0	1	2	3	4
GP3	Because of my physical condition, I have trouble meeting the needs of my family	0	1	2	3	4
GP4	I have pain	0	1	2	3	4
GP5	I am bothered by side effects of treatment	0	1	2	3	4
GP6	I feel ill	0	1	2	3	4
GP7	I am forced to spend time in bed	0	1	2	3	4
	SOCIAL/FAMILY WELL-BEING	Not at all	A little bit	Some -what	Quite a bit	Very much
GS1	I feel close to my friends	0	1	2	3	4
GS2	I get emotional support from my family	0	1	2	3	4
GS3	I get support from my friends	0	1	2	3	4
GS4	My family has accepted my illness	0	1	2	3	4
•						

GS5	I am satisfied with family communication about my illness	0	1	2	3	4
GS6	I feel close to my partner (or the person who is my main support)	0	1	2	3	4
Q1	Regardless of your current level of sexual activity, please answer the following question. If you prefer not to answer it, please mark this box and go to the next section.					
GS7	I am satisfied with my sex life	0	1	2	3	4

